### **4.3 Subject Registration and Prophylactic Treatment Randomization**

Subjects will be recruited from NIH Clinical Center and the surrounding transplant clinics. After confirmation of eligibility and execution of an informed consent, the Principal Investigator or the research nurse will notify the pharmacy of the subject's enrollment and the pharmacy will randomize the subject to therapy. Both investigators and subjects will be blinded to the group assignment until the completion of the study. Assignment of treatment will be done using a block randomization scheme with the assignment probability remaining fixed over the course of the trial. Construction of the randomization schedule is done by pharmacy using a table of random numbers. Subjects will be stratified by the type of conditioning (myeloablative vs. non-myeloablative) to ensure comparable groups.

### **4.4 Recruitment**

Recruitment activities with surrounding transplant clinics will include electronic physician to physician letter distribution, and will include a copy of the recruitment flyer.

## **5. TREATMENT PLAN**

### **5.1 Study Drug Administration**

The study drug or placebo will be dispensed to the subject by the NIH Clinical Center Pharmacy according to the randomization schedule. Treatment assignment will be unknown to subjects, clinical staff and study investigators in order to preserve the blind. Subjects will be instructed to rinse oral cavity 3 times daily for 2 minutes with 10 mL and expectorate. Subjects will also be instructed to avoid eating, drinking, or rinsing

the oral cavity for 30 minutes after administration.

### **5.1.1 Dexamethasone**

Commercially available dexamethasone 0.01% (0.5mg/5 mL) solution will be repackaged, and labeled by NIH Clinical Center Pharmacy under USP <795> guidelines and FDA 503a regulations for the purpose of this study and to allow blinding to subject, clinical staff, and investigators. The study drug supply will be dispensed by the NIH Clinical Center Pharmacy. In case of accidental ingestion, this would be equivalent to about 20 mg of prednisone/day if all 3 doses were swallowed.

### **5.1.2 Placebo**

The placebo rinse (identical to dexamethasone solution in appearance and taste) will also be compounded, labeled, and dispensed by the NIH Clinical Center Pharmacy under USP <795> guidelines and FDA 503a regulations. The placebo rinse will be administered in the same fashion as the dexamethasone rinse.

## **5.2 Permitted Concomitant Medications**

### **5.2.1 *Topical antifungals (clotrimazole)***

Topical corticosteroid treatment is associated with few potential complications. The most common is candidal overgrowth. Subjects will be placed on topical antifungal prophylaxis with clotrimazole 10 mg oral troches 2 times daily for the duration of the intervention to decrease the candidal overgrowth. In subjects unable to tolerate the medication, nystatin swish and spit will be prescribed.

### **5.2.2 *Post transplant medications***

There will be no prohibited interventions for this study except topical agents for oral GVHD. All interventions and medications dictated by the subject's primary transplant protocol and clinical necessity will be permitted. Subjects will be queried at interim assessments regarding topical and systemic analgesic use. Factors that can potentially confound the results (such as systemic steroids and other immunosuppressants) will be tracked and taken into consideration at the time of the final statistical analysis.

## **5.3 Development of Oral Chronic GVHD**

In the event of reaching the primary endpoint (development of clinically significant oral chronic GVHD), the subject will be asked to participate in end of study assessments and then will go off study and treatment options for treating the oral chronic GVHD will be per the transplant team.

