## PRÉCIS

Prevention of oral chronic graft versus host disease (GVHD) by topical agents is an attractive strategy because it would potentially avoid the adverse effects associated with systemic immunosuppression. Topically administered dexamethasone solution is a commonly used agent for the prophylaxis of oral inflammatory conditions including GVHD. However, the efficacy and systemic effects of topically administered dexamethasone solution are unknown. We therefore propose this trial designed to evaluate the efficacy and safety of topical dexamethasone solution for prevention of oral chronic GVHD in stem cell transplant recipients.

This pilot phase II study will follow a randomized, double-blind, placebo controlled, parallel group design. Consenting subjects who have undergone hematopoietic stem cell transplantation at the NIH Clinical Center and the surrounding transplant clinics will be randomized 50/50 to receive dexamethasone 0.01% solution or placebo as an oral rinse for 3 months starting 90-100 days post-transplant. Subjects will be evaluated monthly after the start of intervention. Diagnostic and research evaluations will include a complete oral examination, oral mucosal biopsy prior to the beginning of the intervention (day -7) and at the time of development of oral chronic GVHD or at the completion of intervention in the absence of clinical GVHD. We will measure serum dexamethasone levels and perform short cosyntropin (ACTH stimulation) test at the end of the 3 months of intervention or onset of clinically significant GVHD.

The primary objective of the study is to evaluate the safety and efficacy of topical dexamethasone 0.01% solution used as an oral rinse for prevention of oral chronic GVHD. Our primary endpoint will be the proportion of subjects that develop clinically significant (severity score 3 or higher) oral chronic GVHD after three months.

Secondary objectives will include the impact of oral chronic GVHD on the quality of life, characterization of the changes in tissue and salivary biomarkers associated with development of oral graft versus host disease, and measures of the effects of topical dexamethasone on hypothalamo-pituitary-adrenal axis. Secondary outcomes will include oral cavity specific quality of life as measured by OHIP-14 questionnaire, oral discomfort levels, improvement in general quality of life scores, and severity of oral chronic GVHD as measured by the site-specific GVHD scoring system.

---

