### **6.4 Follow-up Remote Assessment**

If available, after completion of study drug, subjects will be contacted by clinic appointment, phone or email monthly +/- 2 weeks for 5 months: Months 4, 5, 6, 7, and 8. Subjects will be asked to report any symptoms or signs consistent with oral chronic GVHD. In addition, the monthly follow-up remote visits will be used to confirm the absence of oral chronic GVHD symptoms (oral discomfort and xerostomia) and collect the information about the current use of medications. If subject reports symptoms or signs consistent with oral

chronic GVHD, the following will be performed at the time of contact:

- Concomitant meds (immunosuppressive, antimicrobial and analgesics)
- The 0-10 Scale for Oral Pain (see Appendix A)
- The 0-10 Scale for Oral Xerostomia (see Appendix A)
- Patient-assessed Global Scale (perception of changes in oral condition)

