## **6.5 End of Study Assessments (6 months after initiation of oral dexamethasone or diagnosed with oral chronic GVHD)**

After completion of 6 months of follow up, or in the event of symptoms or signs suggestive of oral chronic GVHD, or in case of premature withdrawal from the study and discontinuation of study drug, subjects will return to the Clinical Center for the following end of study assessments:

- Interim assessment including use of immunosuppressive, antimicrobial and analgesic medications
- The 0-10 Scale for Oral pain (see Appendix A)
- The 0-10 Scale for Oral Xerostomia (see Appendix A)
- GVHD Severity Scale (see Appendix B)
- Lichen Planus (Oral GVHD) Severity Scale (see Appendix C)
- Disease specific quality of life - OHIP-14 scale (ages 18 and older only-Appendix D)
- Patient-assessed Global Scale (perception of changes in oral condition)
- Buccal mucosal less than approximately 6mm punch biopsy (18 years or older and if clinically indicated e.g. oral chronic GVHD is suspected)
- Oral photographs (optional)
- Oral lesion documentation
- Research blood sample collection
- Saliva sample collection
- Blood pressure

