### **8.2 Sample Size and Accrual**

07-H-0005

[name].

February 3, 2021

Amendment AA

Using the current overall proportion of clinically significant oral chronic GVHD of 0.25, we note that with 36 patients per arm we would have 80% power to detect the same difference of 30% (15% versus 45%) when testing the difference of proportions at a significance level of 0.05. With amendment R (version date 5-6-2016), we thus propose to reduce the required sample size to 72 subjects. We aim to achieve this new accrual goal within two years and we plan to reassess the futility of protocol if we cannot enroll the expected number of subjects.

**Drop-outs:** In order to maintain appropriate statistical power, subjects who prematurely go off study (i.e. are non-compliant with study requirements or develop oral GVHD in the period between baseline assessments and first dose of study drug) will be replaced. To account for a possible drop-out rate of up to 10%, up to 82 subjects may be accrued. Safety data on drop outs will be included in the safety analysis.

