### 8.5 Data Analyses

This study will be analyzed according to the “intent to treat” principle, that is, all randomized subjects will be included. Subjects not evaluated for endpoints will be considered to have reached the primary endpoint. Every effort will be made to reach and evaluate the subjects at the monthly intervals and at the end of the 3 month intervention period. The differences in proportions of significant oral chronic GVHD will be assessed by a chi-squared test (with continuity correction). Treatment group differences in the severity scores, pain and xerostomia scores, and quality of life scores (OHIP-14) will be assessed using the Wilcoxon test. Adjustments will be made for age and other covariates of interest, such as systemic immunosuppression. Adverse events will be tabulated by severity and treatment assignment. For pediatric subjects, analyses will include growth assessment (growth chart [length for age, weight for age percentiles

and body mass index] for age percentiles) and bone age and the associated z-scores (the number of standard deviations the child's measures [weight, height etc] differ from the population mean).

The intervention period will be 3 months. Should the subject reach the primary endpoint (development of clinically significant oral chronic GVHD), the subject will be asked to participate in end of study assessments and then will go off study. Subjects who did not develop oral chronic GVHD in the intervention phase of the study will be followed for up to 6 months to document late development of oral chronic GVHD. All subjects will be evaluated after 6 months after completion of the intervention phase of the study in the absence of clinical oral GVHD. Final statistical analysis will be performed once all subjects in the sample have completed the study and all records have been collected. We will use stratified analyses to account for effects of systemic immunosuppressive agents and other prognostic factors.

In the event of a protocol violation, the aggregate data will be analyzed with and without those subjects involved in the incident.

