## **8.8 Off Study Criteria**

### **8.8.1 Subject choice:**

Subjects may withdraw from the study at their request any time. The risks of withdrawing will be discussed, as will alternative treatment options. Those subjects who choose to withdraw will be strongly encouraged to participate in post therapy assessments until he/she initiates alternative chronic GVHD therapy or through the 6 month off study medication mark to assess for late occurring adverse events.

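### The passages on adrenal and drug-level testing at early exit contradict each other, and adverse events are tabulated by arm without regard to time observed

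*Combined protocol and SAP*

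**What the plan says.** Sections 5.3 and 8.5 give the same exit rule for a subject who reaches the endpoint: "the subject will be asked to participate in end of study assessments and then will go off study". Section 6.5 defines those assessments and applies the same list to early leavers: in the event of "premature withdrawal from the study and discontinuation of study drug, subjects will return to the Clinical Center for the following end of study assessments". The list includes oral scores, blood pressure, medication use, saliva and research blood. It has no cortisol, ACTH test or dexamethasone level. Section 6.3 has all three.

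The Précis says the investigators will measure dexamethasone levels and "perform short cosyntropin (ACTH stimulation) test at the end of the 3 months of intervention or onset of clinically significant GVHD". Sections 6.6, 8.4.6, 8.8.2 and 10.3.1 each add a further statement on timing; they are set side by side in the working.

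On adverse events, 9.2 starts collection on the first day of study drug and gives no end. The month 1 and 2 contacts (6.2) ask about adverse effects. For months 4 to 8, section 6.4 says "Subjects will be asked to report any symptoms or signs consistent with oral chronic GVHD", asks about medications, and lists no adverse-event question. Section 8.5 says "Adverse events will be tabulated by severity and treatment assignment".

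**The concern.** Safety is part of the primary objective (1.1), and systemic absorption and adrenal effect form secondary objective 1.2.3. Staff who work from the 6.5 list would not draw the samples that other passages expect from a subject who develops GVHD in, say, month 2. The drug-level and adrenal data would then come mainly from subjects still free of the endpoint at month 3. That group is selected after randomisation and, if the rinse works, differently in the two arms.

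The same exit rule makes time under observation depend on the outcome. If fewer dexamethasone subjects reach the endpoint, that arm is observed longer, and a plain count of events by arm does not allow for this.

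**Working it through.** **1. Passages side by side**

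| Section | Test | Timing |
|---|---|---|
| Précis | Dexamethasone level, ACTH test | Month 3 or GVHD onset |
| 6.3 | Cortisol, dexamethasone level, ACTH test (optional) | 3 months +/- 7 days after start |
| 6.5 | None of the three | End of study, suspected oral GVHD, early withdrawal |
| 6.6 | Dexamethasone level, for adherence | End of study assessment |
| 8.4.6 | Morning cortisol; stimulation test if symptoms | Baseline, monthly visits at NIH, and completion of the intervention, which it dates 3 months after the last dose |
| 8.8.2 | Evaluations on leaving study drug, not specified | Subjects taken off study, including endpoint cases |
| 10.3.1 | Adrenal function, test not named | End of prophylaxis |

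These cannot all be followed. They disagree on whether an endpoint case before month 3 is tested, and on whether the ACTH test is for everyone, optional or driven by symptoms.

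**2. Design rates (8.2)**

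Inputs: 15% vs 45%, significance level 0.05, 80% power, 36 per arm. The arms are not labelled; under the hypothesis in 8.1.1 the higher rate is taken as placebo. Assuming a two-sided test without continuity correction:

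n = [1.96 × √(2 × 0.30 × 0.70) + 0.842 × √(0.15 × 0.85 + 0.45 × 0.55)]² / 0.30² = (1.270 + 0.516)² / 0.09 = 35.4, so 36 per arm. The plan's figure is reproduced.

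**3. Subjects without the tests if the 6.5 list is followed**

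- Upper bound (every endpoint found before the 6.3 visit): 0.15 × 36 = 5.4 on dexamethasone and 0.45 × 36 = 16.2 on placebo. That leaves 30.6 and 19.8 with the tests available.
- Lower bound (every endpoint first scored at month 3): 0 and 0.
- At the pooled rate of 0.25 reported in 8.2, the upper bound is 0.25 × 72 = 18 in total: 3.6 and 14.4 at 10% vs 40%, 7.2 and 10.8 at 20% vs 30%, 9 and 9 at equal rates.

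**4. Mean time observed**

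Mean months = p × t + (1 − p) × T, where p is the endpoint rate, t the mean endpoint time (assumed; the plan gives none) and T the end of observation. Other losses, and endpoints after month 3, are ignored.

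| T | t | Dexamethasone | Placebo | Ratio |
|---|---|---|---|---|
| 3 (on drug) | 3 | 3.0 | 3.0 | 1.00 |
| 3 (on drug) | 1.5 | 2.775 | 2.325 | 1.19 |
| 9 (drug plus 6 months) | 3 | 8.1 | 6.3 | 1.29 |
| 9 (drug plus 6 months) | 1.5 | 7.875 | 5.625 | 1.40 |

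Sensitivity:
- All endpoints at month 1, an extreme case: on-drug 2.7 / 2.1 = 1.29.
- The 6.5 heading dates the end of study 6 months after initiation, whereas 8.5 has 6 months after the intervention. With T = 6 the ratios are 5.55 / 4.65 = 1.19 (t = 3) and 5.325 / 3.975 = 1.34 (t = 1.5).
- At 20% vs 30% with t = 1.5: on-drug 2.7 / 2.55 = 1.06; to month 9, 7.5 / 6.75 = 1.11.
- At equal endpoint rates every ratio is 1.00.

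**The case against.** Three stronger readings are tempting, and the documents do not support them.

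*The plan simply omits testing at exit.* A reader of 6.5 alone might infer this. But the Précis, 6.6, 8.8.2 and 10.3.1 all point to some testing at exit or at the end of prophylaxis. Section 8.8.2 asks endpoint cases for two sets of evaluations, and the natural counterparts are the 6.3 and 6.5 lists. The intent to test is visible; the visit list does not carry it out. Months 1 and 2 may also be handled by phone or email (6.2), and the first scheduled post-baseline Appendix C score is at month 3. Many endpoints may therefore be found at a visit where the 6.3 tests are taken.

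*Placebo is observed much less, so raw counts will show a false excess on dexamethasone.* The ratios of 1.29 to 1.40 need adverse events to be collected for six months off drug, which the month 4 to 8 contacts do not provide for. Sections 9.2 and 9.3 also restrict capture, largely to severe events or to related events beyond the label, and send transplant complications to the transplant protocol. A constant monthly event rate to month 9 fits that rule poorly. What stands is that the length of observation depends on outcome and that no end of collection is written.

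*Voluntary withdrawers are followed better than endpoint cases.* Section 8.8.1 does encourage their assessment "through the 6 month off study medication mark to assess for late occurring adverse events". The same sentence lets it stop when alternative chronic GVHD therapy begins, and endpoint cases are the subjects handed over for such treatment. Systemic steroids would also confound later adrenal findings, as 8.4.6 recognises. The contrast does not hold.

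Tabulating adverse events by arm is not an error in itself; the objection is to giving nothing beside it.

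**Conclusion.** The point holds as an internal contradiction with a limited consequence for safety data, and it should be corrected. Following the 6.5 list literally could cost objective 1.2.3 the tests on anything from no subjects to about 5 of 36 on dexamethasone and 16 of 36 on placebo. The loss in the dexamethasone arm, which matters for absorption, is small. The imbalance matters more for comparing adrenal function between arms. The upper figures rest on the 15% vs 45% design rates, on every endpoint falling before the month-3 visit, and on the other passages being disregarded.

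For adverse events, the supportable imbalance is in on-drug time: modest for endpoints averaging month 1.5 and absent if they are found at month 3. It becomes larger only if collection runs into the off-drug period or endpoints come very early. It disappears if the two arms have the same endpoint rate and timing.

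**What to change.** 1. Reconcile the Précis, 6.3, 6.5, 6.6, 8.4.6, 8.8.2 and 10.3.1 into one test schedule. The 6.3 cortisol and dexamethasone samples, and the ACTH test (optional in 6.3), should be addressed explicitly for early exit so that the visit list agrees with what the Précis already states. The sponsor should settle on what basis the ACTH test is done, define the evaluations named in 8.8.2, and align the timing in 8.4.6.
2. State in 9.2 when adverse-event collection ends, for completers and for early leavers.
3. In 8.5, report adverse events by arm for the on-drug period and per person-month observed, alongside the planned counts.

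Cost: wording changes, one blood sample at a visit that already draws research blood, and a little more analysis. The rate calculation needs only start and exit dates. Longer follow-up of endpoint cases after new GVHD therapy is not needed for this correction.

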## **5.4 Management of Complications**

### **5.4.1 *Oral candidiasis***

If oral candidiasis develops despite clotrimazole prophylaxis, standard treatment will be administered.

### **5.4.2 *Adrenal suppression***

Asymptomatic subjects without clinical signs of adrenal insufficiency and abnormal ACTH and/or cortisol test results at the end of the intervention period may be observed without steroid replacement and retested in 1 month. In case of development of symptoms suggestive of adrenal suppression (such as abdominal pain, nausea and vomiting, fatigue and hypotension) subjects will then be placed on the standard maintenance replacement regimen of the corticosteroids such prednisone 5-7.5 mg once daily and reevaluated in 1 month

by ACTH testing. All subjects with the abnormal ACTH test results will be advised of the symptoms and signs of clinically significant adrenal suppression and will be given stress doses of hydrocortisone injections for emergencies and a wrist bracelet.

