### **6.3 End of Treatment Monitoring and Assessments (3 months)**

Subjects will be evaluated at the NIH at 3 months (+/- 7 days) after starting study medication with the following assessments:

- Interim assessment
- Blood pressure
- Concomitant meds (immunosuppressive, antimicrobial and analgesics)
- The 0-10 Scale for Oral Pain (see Appendix A)
- The 0-10 Scale for Oral Xerostomia (see Appendix A)
- Patient-assessed Global Scale (perception of changes in oral condition-Appendix A)
- GVHD Severity Scale (see Appendix B)
- Lichen Planus (oral GVHD) Severity Scale (see Appendix C)
- Disease specific QOL- OHIP-14 scale (ages 18 and older only) (Appendix D)
- Complete blood count (CBC with diff) – done concurrently with post transplant monitoring
- Serum chemistry (Acute Care (Na, K, Cl, CO2, Creatinine, Glucose, and Urea Nitrogen), Mineral (Phosphorus, Magnesium, Albumin, and Calcium), Hepatic (Alk Phosphatase, ALT, AST, Total Bilirubin, and Direct Bilirubin), and Other (Total Protein, CK, Uric Acid, and LD) panel) – done concurrently with post transplant monitoring
- Serum cortisol level (results blinded to investigators)
- ACTH stimulation test (Optional)
- Serum dexamethasone level (results blinded to the investigators)
- Buccal mucosal less than approximately 6mm punch biopsy ages 18 and older only (optional)
- Oral photographs (Optional)
- Oral lesion documentation
- Research blood sample collection
- Saliva sample collection
- Growth chart (length for age, weight for age percentiles and body mass index for age percentiles, pre-pubertal children) (if hand x-ray is available on parent transplant protocol, the results will be reviewed)

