#### 8.4.6 Assessment of adrenocortical function (cortisol levels)

Subjects will be evaluated for possible hypothalamic-pituitary axis (HPA) axis suppression with the following measures:

1. Morning cortisol levels will be determined at baseline, monthly follow-ups (done at NIH), and at completion of the interventional phase (3 months after the last dose of study medication). The results will be blinded to the investigators until the end of the study. At the end of the study, in subjects with morning cortisol levels between 19 mcg/dL and 3 mcg/dL no further adrenal function testing will be performed.
2. In subjects with the symptoms of suspected adrenal insufficiency, a Short Cosynthropicin Test (SCT) will be performed to determine if the subject has HPA axis suppression. In brief: venous blood will be collected before administration of 250 mcg of cosyntropicin (synthetic ACTH) around 8 AM to 12 noon, and at 30 and 60 minutes after. The expected rise in cortisol levels is to at least 18 mcg/dL (24). In cases of minimally abnormal SCT (stimulated cortisol values of 13-17 mcg/dL), the test will be repeated the next day, as it has been demonstrated that the result is often normal with a repeat test. This test has been shown to be sensitive and specific for evaluation of subclinical adrenal suppression [52, 53]. In the unlikely event of significant adrenal suppression as assessed by repeat ACTH stimulation test, Clinical Center Endocrinology Service will be consulted. Pharmacy will be requested to unblind therapy to the endocrinologist so that appropriate therapy can be initiated and the endocrinologist can appropriately attribute the relationship of the event to study drug administration.
3. The confounding effect of systemic corticosteroids will be taken into account at the time of analysis. We expect to have a subgroup of subjects who will not receive systemic steroids. This subgroup will be used to evaluate the effects of topical dexamethasone on adrenal secretion.

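### For an asymptomatic subject without the optional ACTH test, the 1-month retest in 5.4.2 cannot follow an abnormal month-3 cortisol on time, because no one is named to see the blinded result

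*Combined protocol and SAP*

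**What the plan says.** **Action rule.** Section 5.4.2 says that asymptomatic subjects with "abnormal ACTH and/or cortisol test results at the end of the intervention period may be observed without steroid replacement and retested in 1 month". Replacement steroid starts "In case of development of symptoms suggestive of adrenal suppression". The closing sentence covers a narrower group: "All subjects with the abnormal ACTH test results will be advised of the symptoms and signs of clinically significant adrenal suppression". Emergency hydrocortisone and a bracelet go to that same group.

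**Tests at the end of treatment.** Section 6.3 sets the visit: "Subjects will be evaluated at the NIH at 3 months (+/- 7 days) after starting study medication". Its list includes "Serum cortisol level (results blinded to investigators)" and, as a separate item, "ACTH stimulation test (Optional)". The ACTH item carries no blinding note.

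**Blinding and timing of cortisol.** Section 8.4.6 says of morning cortisol: "The results will be blinded to the investigators until the end of the study". It mentions using cortisol values to decide on further testing only at the end of the study. It places the last sample "at completion of the interventional phase (3 months after the last dose of study medication)". It calls for the cosyntropin test when symptoms raise suspicion. Endocrinology is consulted, and may learn the treatment arm from pharmacy, only once a repeat stimulation test shows significant suppression.

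**Background.** The Précis describes the cosyntropin test as if every subject had it. Section 2.5 says that absorption from the rinse has not been studied and that suppression is likely if it is significant. Section 10.3.1 calls suppression very rare, sees no need for routine symptom monitoring, and points to blood pressure at visits and an adrenal assessment when prophylaxis ends.

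**The concern.** A rule that acts on a test result needs someone who can see the result while there is time to act. Section 5.4.2 acts on cortisol; 6.3 and 8.4.6 withhold cortisol from the people who would act. The ACTH test could fill the gap, but it is optional for a subject with no symptoms. A subject who does not take it has one adrenal result at the end of treatment, and nobody is assigned to read it in time.

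That subject also falls outside the symptom advice, which depends on an abnormal ACTH test. The monthly contacts in 6.4 may be by telephone or email and ask about oral GVHD symptoms and medication, not adrenal symptoms.

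Safety is half of the primary objective, and adrenal effect is the systemic risk for which the plan writes a specific management rule. What is at stake is one safety step and the advice that should go with it. No efficacy estimate is affected.

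**Working it through.** The plan states no figure to reproduce. The check has three parts.

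**1. Who can see which result, and when**

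| Asymptomatic subject at month 3 | Result visible in time? | Retest possible at 1 month? | Symptom advice under 5.4.2? |
|---|---|---|---|
| ACTH test done, abnormal | Yes (6.3 does not mark it blinded) | Yes | Yes |
| ACTH test done, normal; serum cortisol abnormal | Cortisol: no | Not from the cortisol | No |
| No ACTH test; serum cortisol abnormal | No | No | No |

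The third row is the one that matters, because nothing else measures that subject's adrenal function. I looked for any other recipient of the cortisol. The only disclosure route in 8.4.6 gives the treatment arm, not cortisol values, to the endocrinologist, and only after a repeat ACTH test. Section 9.1 gives the DSMB progress reports at an interval still to be set. Neither is assigned to read the cortisol.

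**2. Timing, in months from the start of study drug**

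Inputs: treatment ends at month 3 and the sample is taken then (6.3); the retest is 1 month later (5.4.2). For a subject who completes follow-up, the end of study is month 6 by the heading of 6.5, which counts from the start of drug. By 8.5 and 8.8.3, which count six months from the end of treatment, it is 3 + 6 = month 9.

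- Retest due: 3 + 1 = month 4.
- Release under the 6.5 heading: 6 − 4 = 2 months after the retest is due.
- Release under 8.5 and 8.8.3: 9 − 4 = 5 months after.
- If the end of the study means the end of the whole trial, release is later still for everyone except the last subjects to finish.

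**3. The conflicting sample time in 8.4.6**

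Taken literally, three months after the last dose is 3 + 3 = month 6, and a retest would fall at 6 + 1 = month 7. Release would then come between 6 − 7 = −1 (one month before) and 9 − 7 = +2 (two months after). This reading does not rescue the rule. Section 5.4.2 concerns results at the end of the intervention, and a month-6 sample is not one: it would measure adrenal function three months after exposure stopped. The same clause of 8.4.6 also describes the sample as falling at completion of the interventional phase, so it conflicts with itself as well as with 6.3.

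**The case against.** **The retest is permissive.** This stands. Section 5.4.2 says that subjects may be observed and retested; its main work is to allow replacement to be withheld. A reader might infer that a mandatory safety step is breached. The text does not support that: the plan allows a step that it then gives no one the means to take.

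**Cortisol in 5.4.2 could mean the stimulated values from the cosyntropin test.** Those are cortisol measurements and are not marked as blinded, so on this reading the retest works. It cannot be excluded, but 5.4.2 names ACTH and cortisol results separately and 6.3 lists them as two tests.

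**The blinding is deliberate.** A low cortisol hints at dexamethasone, and oral GVHD is scored by investigators. This is a good reason to keep the value from the scorers. It is not a reason for nobody to read it.

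**Other cover exists.** A reader might infer that adrenal suppression would go undetected altogether. The documents do not support that. Symptoms lead to testing (8.4.6) and replacement (5.4.2). Blood pressure and serum chemistry, including sodium, potassium and glucose, are listed at month 3 without a blinding note. The month 1 and 2 contacts ask about adverse effects, and subjects are under post-transplant care. This narrows the gap but does not close it, because the retest rule was written for subjects without symptoms.

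**A low morning cortisol is non-specific.** This also stands. Section 8.4.6 recognises systemic steroids as a confounder and expects only a subgroup to be free of them. Tying emergency hydrocortisone and the bracelet to the stimulation test is defensible.

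**Conclusion.** The point holds in a limited form. For an asymptomatic subject who does not have the optional ACTH test, the cortisol part of 5.4.2 cannot be carried out on time: the result is released 2 or 5 months after the retest is due, at the earliest. The symptom advice does not reach this subject either. Separately, 8.4.6 contradicts 6.3 on when the cortisol is taken.

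This rests on three assumptions: the sample is taken at month 3 as scheduled in 6.3; cortisol in 5.4.2 includes the serum level; and the subject completes follow-up. Someone who leaves the study early could have an earlier end of study, if that phrase is read per subject.

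The number affected cannot be sized, since the documents give neither a rate of abnormal cortisol nor the uptake of the ACTH test. If every subject had that test, as the Précis implies, the third row of the table would be empty.

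Two further inferences should be resisted. Release is late in three of the four pairings of sample time and end of study, but that counts readings of the text; it is not a probability or a share of subjects. And 3 mcg/dL is not an alert limit in this plan: 8.4.6 says only that values between 3 and 19 mcg/dL get no further testing, and applies that at the end of the study.

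I would treat this as a cheap safety improvement that should be made.

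**What to change.** 1. **Name a reader (5.4.2 and 8.4.6).** Release the month-3 morning cortisol, when available, to an existing person who does not score oral GVHD, for example in the Clinical Center Endocrinology Service. Endocrinology sets the alert limit and takes systemic steroid use into account. That person arranges the symptom advice and the 1-month retest without disclosing the arm.
2. **Widen the advice (5.4.2).** Extend the symptom advice to subjects with an abnormal cortisol. Leave emergency hydrocortisone and the bracelet tied to the ACTH test or to endocrinology's judgement.
3. **Correct the timing (8.4.6).** State that this cortisol is taken at the 3-month end-of-treatment visit in 6.3.

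Cost: changes of wording, and no test beyond the retest already allowed. The recipient takes on a small added role, since endocrinology now enters only after a repeat ACTH test. There is a limited unblinding risk because a low value may suggest dexamethasone. It is confined to someone who does not score the outcome, and is weakened further because systemic steroids also lower cortisol.
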